### 6.4 Level of Significance, Multiple Comparisons and Multiplicity

All statistical hypotheses will be two-sided and will be performed using a 5% significance level.

No adjustment for multiple comparisons or corrections for multiplicity are foreseen.

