## **2.2 Rationale for the Study**

Cataract surgery is one of the most common surgical procedures performed worldwide. In fact, in 2017, 3.8 million cataracts procedures were performed in the US.

Despite of surgical advances, pain and inflammation after ophthalmic surgery continues to be a burden on both patients and physicians. The treatment of postoperative pain is essential for hospitalized patients, but it is even more important for patients who are treated on an outpatient basis.

Also, pain after ophthalmic surgery may be considered a sign of a possible complication. Severe pain is assumed to be a sign of postoperative inflammation or infection, making it a concern for both patient and physician. However, a surgery without perioperative complications may also be associated with significant postoperative pain during the early

recovery. Thus, appropriate counseling and pain management should be provided to improve quality of life.

Clobetasol propionate ophthalmic nanoemulsion 0.05% will be administered as a topical ophthalmic nanoemulsion.

Patients are expected to self-administer one drop of either clobetasol propionate ophthalmic nanoemulsion 0.05% or placebo control QID.

Direct instillation is the most efficient method for delivery to the ocular surface and is an accepted and widely used method for topical application to the eye. This study will examine effect and tolerability for 14 days of clobetasol propionate ophthalmic nanoemulsion 0.05% dosed QID.

This study is being conducted to support an application for approval to market clobetasol propionate ophthalmic nanoemulsion 0.05% in the US for the indication of inflammation and pain after ocular surgery. The reference (comparator) product in this study, the vehicle, is expected to provide a lower efficacy rate when compared to clobetasol 5%.

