#### 9.1.1 *Sample Size*

A two group  $\chi^2$  test with a 0.05 two-sided significance level will have 80% power to detect the difference between a proportion with complete resolution of anterior chamber cells in the active group of 0.22 and the placebo group proportion of 0.07 (odds ratio of 3.747) when the sample size is 202. Considering a 4% lost to follow-up rate a final sample size of 210 patients will be required (140 clobetasol, 70 placebo, in a 2:1 randomization ratio).

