### **9.1.11 Key Secondary Analysis**

The aim of the key secondary analysis of this study is to assess the superiority of clobetasol propionate ophthalmic nanoemulsion 0.05% compared to placebo with respect to the key secondary endpoint in the FAS.

The key secondary analysis will be based on a single study eye for each patient. Each patient's study eye will be defined as the surgery eye.

The test will be the proportion of study eyes with no pain (pain = 0) at Visit 3 (Day 8 ± 1 day) without receiving rescue medication as compared between clobetasol propionate ophthalmic nanoemulsion 0.05% dosed QID and placebo dosed QID using the chi square statistic.

The PP population set will be also tested to confirm the robustness of the key secondary analysis.

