## 9.2 Changes in Statistical Methods

Any deviation(s) from the original statistical analysis plan (as described in the study protocol or in the SAP) will be described and justified in a protocol amendment and/or in a revised SAP and/or in the final report, as appropriate.

If, after the study has begun, but prior to any unmasking, changes are made to primary hypothesis, or the statistical methods related to this hypothesis, then the protocol will be amended (consistent with ICH Guideline E-9). Changes to other non-confirmatory analyses made after the protocol has been finalized, along with an explanation as to when and why they occurred, will be listed in the CSR for the study. Post hoc exploratory analyses will be clearly identified in the CSR.

---

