#### 3.2 Secondary Efficacy Endpoints

Key secondary efficacy endpoint

- Proportion of patients with VAS pain score of “0” (no eye pain) compared to placebo at Day 8.

Eye pain score will be assessed by the patient before any ocular examination and will be scored by ticking on a continuous scale comprised of a 10 cm horizontal line anchored by two verbal descriptions: “no eye pain” (score of 0) and “worst imaginable eye pain” (score of 10).

- Proportion of patients with anterior chamber cell grade of “0” compared to placebo at Day 3, Day 15 and Day 29.

- Change from Baseline to Day 3, Day 8, Day 15 and Day 29 compared to placebo in the proportion of patients with different anterior chamber cell grades.
- Change from Baseline to Day 3, Day 8, Day 15 and Day 29 compared to placebo in the proportion of patients with different anterior chamber flare grades.
- Proportion of patients with anterior chamber cell grade of “≤0.5+” and flare grade of “0” compared to placebo at Day 3, Day 8, Day 15 and Day 29.
- Proportion of patients with anterior chamber cell grade of “≤1+” compared to placebo at Day 3, Day 8, Day 15 and Day 29.
- Proportion of patients with anterior chamber cell grade of “0” and flare grade of “0” compared to placebo at Day 3, Day 8, Day 15 and Day 29.
- Frequency of different signs of ocular inflammation compared to placebo at Baseline, Day 3, Day 8, Day 15 and Day 29.
- Change from Baseline to Day 3, Day 8, Day 15 and Day 29 compared to placebo in the proportion of patients with different signs of ocular inflammation.
- Change from Baseline to Day 3, Day 8, Day 15 and Day 29 compared to placebo in the severity of signs of ocular inflammation.
- Change from Baseline to Day 3, Day 8, Day 15 and Day 29 compared to placebo in the visual analog scale (VAS) photophobia score.
- Change from Baseline to Day 8, Day 15 and Day 29 compared to placebo in Snellen best-corrected visual acuity (BCVA) score.
- Change from Baseline to Day 3, Day 8, Day 15 and Day 29 compared to placebo in the VAS pain score.
- Proportion of patients with VAS pain of “0” compared to placebo at Day 3, Day 15 and Day 29.
- Change from baseline to Day 3, Day 8, Day 15 and Day 29 compared to placebo in the proportion of patients with different discomfort grades.
- Proportion of patients with no discomfort (“None”) compared to placebo at Day 3, Day 8, Day 15 and Day 29.
- Change over time in the VAS pain score reported in the patients’ diaries compared to placebo.

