### **6.3.6 Secondary Efficacy Analyses**

#### **6.3.6.1 Key Secondary Efficacy Analysis**

The key secondary efficacy endpoint is the proportion of patients with VAS pain score of "0" (no eye pain) compared to placebo at Day 8.

The key secondary analysis will be based on a single study eye for each patient. Each patient's study eye will be defined as the surgery eye.

A Chi-Square test will be performed to test the proportion of study eyes with no pain (VAS = 0) at Visit 3 (Day 8 ± 1 day) without receiving rescue medication as compared between clobetasol propionate ophthalmic nanoemulsion 0.05% dosed QID and placebo dosed QID. The proportion of eyes with no pain together with its 95% confidence interval (CI) will be presented.

Analysis will be conducted both in FAS and PP to test the robustness of the results.

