### 6.3.6.2 Secondary Analysis

The secondary efficacy endpoints are described in Section 3.2. All secondary efficacy endpoints defined in this section will be analysed as exploratory.

For categorical variables, a summary of these endpoints will be presented at each specified timepoint by treatment group and will include the number and percentage of each category with the 95% CI. A chi-square test or Fisher Exact test, as appropriate will be performed to compare proportions between treatments at each timepoint.

For continuous variables: VAS photophobia, Snellen best-corrected visual acuity (BCVA) score and VAS pain score, a summary of these endpoints will be presented at each specified timepoint by treatment group. Change from baseline will be derived and presented in the same way.

For variables: Anterior chamber cell grades, anterior chamber flare grades, severity of signs of ocular inflammation and eye discomfort grades categorical and continuous summary statistics will be presented, changes from baseline will also be derived and will be presented as increase, decrease or not change table. In the same way, a table with 2 categories: Improvement and no improvement (increase+no change) will be presented. A chi-square test or Fisher Exact test will be performed to compare proportions between treatments:

Change from baseline to Day 3		
Anterior Chamber Cell Grade	IMP	Placebo
Decrease (Improvement)	n (%)	n (%)
No change	n (%)	n (%)
Increase (Worsening)	n (%)	n (%)
P value chi-square or Fisher	p-value	
Improvement	n (%)	n (%)
No Improvement	n (%)	n (%)
	p-value	

No Improvement = increase + no change

For the variables mentioned above, to see the proportion of patients with different grades, a descriptive table like the following will also be built, no statistical inference will be made:

Grade	IMP			Placebo		
	Baseline	Day X	Change	Baseline	Day X	Change
0	n (%)	n (%)	(%)	n (%)	n (%)	(%)
0.5+	n (%)	n (%)	(%)	n (%)	n (%)	(%)
1+	n (%)	n (%)	(%)	n (%)	n (%)	(%)
2+	n (%)	n (%)	(%)	n (%)	n (%)	(%)
3+	n (%)	n (%)	(%)	n (%)	n (%)	(%)
4+	n (%)	n (%)	(%)	n (%)	n (%)	(%)

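### No testing order is set between the primary (cell grade 0) and the key secondary (VAS pain 0), so the plan as written allows a pain superiority claim after a failed primary

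*SAP*

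**What the plan says.** SAP 6.4 sets one rule for all hypotheses, a two-sided 5% level, and adds: "No adjustment for multiple comparisons or corrections for multiplicity are foreseen". Protocol 9.1 likewise uses two-sided 0.05 by default.

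Pain has a confirmatory-sounding aim of its own. Protocol 9.1.11 says: "The aim of the key secondary analysis of this study is to assess the superiority of clobetasol propionate ophthalmic nanoemulsion 0.05% compared to placebo", for the key secondary endpoint in the FAS. SAP 6.3.6.1 carries this out: "A Chi-Square test will be performed to test the proportion of study eyes with no pain (VAS = 0) at Visit 3". Protocol 9.1.10 and SAP 6.3.5 do the same for the primary. None of these sections refers to the result of the other test.

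Protocol 2.2 explains the purpose: the trial supports an application "in the US for the indication of inflammation and pain after ocular surgery". Pain is part of the indication sought, and SAP 8.1 marks the FAS tables for both endpoints as top-line output.

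SAP 6.3.6.2 adds a second uncertainty: "The secondary efficacy endpoints are described in Section 3.2. All secondary efficacy endpoints defined in this section will be analysed as exploratory". Section 3.2, to which it points, opens with the item headed "Key secondary efficacy endpoint".

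**The concern.** Two endpoints each have a superiority aim and a test at the full 5%, and the section meant to govern multiplicity contains no order, gate or split. The labels primary and key secondary suggest a ranking, but a label does not say what follows when the first test fails and the second succeeds.

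The consequence depends on a choice the documents do not make. If a win on either endpoint could support a claim within the indication, the chance of at least one false claim is above that of a single test. If both must succeed, the joint claim is not inflated. The plan does not say which applies.

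A failed primary is a realistic event. Protocol 9.1.1 states that the trial "will have 80% power to detect the difference between a proportion with complete resolution of anterior chamber cells" under its assumed rates, so the primary fails in about one trial in five even when those rates are true. The plan does not say how a pain result with p < 0.05 should be read in such a trial.

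**Working it through.** **Inputs.** Two-sided alpha 0.05 for each test (Protocol 9.1, SAP 6.4). Response rates 0.22 and 0.07, 202 evaluable patients, 2:1 allocation, 80% power (Protocol 9.1.1). The documents give no correlation between the two endpoints, so it is assumed over the range 0 to 0.9. They give no Day 8 pain rates by arm, so power for pain cannot be computed.

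**1. The plan's own power figure.** Split 202 as 135 and 67 and use the pooled-variance normal approximation to the chi-square test.

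- Pooled rate: (135 × 0.22 + 67 × 0.07) / 202 = 34.39 / 202 = 0.1702
- SE under the null: √[0.1702 × 0.8298 × (1/135 + 1/67)] = 0.0562
- SE under the alternative: √(0.22 × 0.78/135 + 0.07 × 0.93/67) = 0.0474
- Power: Φ[(0.15 − 1.96 × 0.0562) / 0.0474] = Φ(0.84) = 0.800

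The stated 80% is reproduced. The chance that the primary fails at the assumed effect is 1 − 0.80 = 0.20.

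**2. Error over the two tests, both nulls true.** At correlation 0:

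- At least one rejection in either direction: 1 − 0.95² = 0.0975
- At least one false win for clobetasol: 1 − 0.975² = 0.0494
- Both false wins for clobetasol: 0.025² = 0.0006

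At other correlations the values come from the bivariate normal distribution with critical value 1.96. The last column is the specific event at issue, a false pain win without a primary win: 0.025 minus the chance that both win.

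| Assumed correlation | At least one, two-sided | At least one in favour | Both in favour | Pain in favour, primary not |
|---|---|---|---|---|
| 0 | 9.75% | 4.94% | 0.06% | 2.44% |
| 0.3 | 9.51% | 4.76% | 0.24% | 2.26% |
| 0.5 | 9.07% | 4.54% | 0.46% | 2.04% |
| 0.7 | 8.35% | 4.17% | 0.83% | 1.67% |
| 0.9 | 7.04% | 3.52% | 1.48% | 1.02% |
| One test alone | 5% | 2.5% | – | – |

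If both endpoints must win, the error in favour is the fourth column when both nulls are true. When only one null is true it is at most 2.5%, the chance that the null endpoint wins falsely.

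**3. Error under a fixed sequence.** Test the primary at 0.05, and test pain at 0.05 only after a primary win for clobetasol.

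- If the primary null is true, any false claim needs a primary rejection first: at most 5% two-sided, 2.5% in favour.
- If the primary null is false and the pain null true, the only possible false claim is on pain: again at most 5% and 2.5%.

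This holds at any correlation. The primary keeps its full alpha, so N and power do not change. By comparison, splitting alpha as 0.025 and 0.025 would cut primary power at N = 202 from about 80% to 69.6%.

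**The case against.** The best defence is that the documents already treat the primary as the one confirmatory hypothesis. SAP 6.3.5 writes out null and alternative hypotheses for the primary only, the sample size rests on the primary only, and Protocol 9.2 speaks in general terms of other, non-confirmatory analyses. The multiplicity sentence also does not forbid a fixed sequence, since that procedure tests each endpoint at the full 5% without adjustment. The indication is worded jointly, and if both endpoints must win there is no inflation. Finally, the two-sided 9.75% counts results favouring placebo and includes the primary's own 5%. Independence is also a doubtful lead case, because rescue counts as failure on both endpoints.

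Much of this is fair and limits the size of the point. The in-favour columns are the ones that matter for a superiority claim, and the inflation exists only if either win suffices. The 20% is the primary's type II error, and how often a significant pain result would accompany it is unknown.

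The gap remains. The phrase in Protocol 9.2 does not classify the key secondary, which Protocol 9.1.11 gives a superiority aim. Compatibility with a fixed sequence does not supply one. If the word exploratory in SAP 6.3.6.2 were meant to cover pain, it would sit badly with that aim. The separate heading 6.3.6.1 suggests it covers only the other secondary endpoints, but the cross-reference to Section 3.2 leaves this open.

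**Conclusion.** The concern holds. No order, gate or alpha split between the two superiority tests appears in either document, so the plan followed as written permits a pain superiority claim after a failed primary.

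The size is conditional. If either win sufficed and both nulls were true, the chance of a false win for clobetasol would be about 1.4 to 2 times the single-test level (3.52/2.5 to 4.94/2.5) over assumed correlations of 0.9 to 0. If both must win, it stays at or below 2.5%. The primary's error rate, power and sample size are not affected. That the rule is missing is certain from the text. What it would cost depends on a claim rule that the documents leave unstated. This should be corrected before unmasking, because an order chosen afterwards could look driven by the data.

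**What to change.** Before unmasking:

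- **SAP 6.4 and 6.3.6.1:** state that the primary is tested first in the FAS at two-sided 0.05. Only if it is significant in favour of clobetasol is VAS pain 0 at Day 8 tested in the FAS at two-sided 0.05 as confirmatory. Otherwise the pain result is reported as descriptive.
- **SAP 6.3.6.2:** state that exploratory status applies to the secondary endpoints other than the key secondary.
- **Protocol 9.1.11:** align it with the same rule. Protocol 9.2 provides the route, since deviations from the planned analysis "will be described and justified in a protocol amendment and/or in a revised SAP and/or in the final report".

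The sequence controls the error whether one win or both are needed for a claim, so it does not have to wait for that decision.

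The cost is a short SAP revision and a matching protocol change, with IRB approval under Protocol 11.4 if it is made as a major amendment. There are no extra patients and no loss of primary alpha or power. The real price is that a pain result cannot be confirmatory when the primary fails, which has a 20% chance at the planned power. A confirmatory claim is actually lost only in those of the failed trials where pain would have been significant.

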### 6.5 Adjustment for Covariates

Baseline value will be used as a covariate in the MMRM analyses for the continuous secondary efficacy endpoints (see Section 6.3.6).

### 6.6 Handling of Dropouts and Missing Data

No missing imputation methods are foreseen. As described in the CSP, any missing, unused, or spurious data will be noted in the final Clinical Study Report (CSR) and presented in the data listings.

In all listings, missing or incomplete dates should be left as they have been recorded. However, for calculation / sorting / assignation based on dates, the following method will be

used, in the event that any date is incomplete after Data Management processing and this date needs to be used for calculation:

- if no field is available: no imputation will be performed,
- if only the year is available: Day “01” and month of “July” will be imputed,
- if the month and year are available: Day “15” will be imputed.

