#### **6.2.2 Dose and Treatment Regimens in the Study**

The IMP will be administered as ophthalmic treatment.

The proposed clinical posology is one drop (0.03 mL) of IMP into the affected eye QID for a 14-day treatment period. Doses should be administered approximately 6 hours apart.

This posology is selected based on pre-clinical data of clobetasol propionate ophthalmic micronized. Systemic HED in the rabbit study was 17-times higher compared to dosing in one eye of adults.

Accordingly, the suggested dose for this study is aligned with current efficacy and safety-proved doses of clobetasol.

If a patient's medication is lost by breakage or spillage, the investigator will retrieve the replacement medications and communicate to Sponsor. The reason why the replacement medication has been used should be documented on the eCRF "Comments Form".

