## 6.3 Hypotheses and Statistical Methods

### 6.3.1 Definitions

Baseline	( Visit 1 (Day 1, 24 h after the cataract surgery).
Time calculation	Differences between dates to express duration will be calculated as the final date - initial date + 1. To convert these days differences to other units, the following conversion factors will be used: 1 year = 365.25 days and 1 month = 30.4375 days.  Ex. Age = (informed consent date – date of birth + 1) / 365.25
Absolute change from Baseline	Absolute change from Baseline at Visit X will be calculated as:  Absolute change from Baseline = Visit X - Baseline
Percentage change from Baseline	Percentage change from Baseline at Visit X will be calculated as:  Percentage change from Baseline [%] = ((Visit X - Baseline)/Baseline) *100  In case of Baseline = 0 no percentage change from baseline will be calculated.
Signs of ocular inflammation (yes/no)	The presence/absence of the different signs of ocular inflammation: Chemosis, Bulbar conjunctival injection, ciliary injection, corneal edema, keratic precipitates will be defined as:  No: grade=0 (absence)  Yes: grade=1, 2 or 3 (presence)
Conversion Snellen to LogMar	Step 1. Mar = Snellen Denominator/Snellen Numerator  Step 2. LogMar = log (Mar)  Example: Snellen 20/40  Mar = 40/20 = 2  LogMar= log(2) = 0.3
Treatment Emergent Adverse Event	Treatment Emergent Adverse Events (TEAEs) are defined as an event that emerges during treatment  having been absent pre-treatment or worsens relative to the pre-treatment state:  First dose IMP/Pacebo date ≤ start date AE ≤ last dose IMP/Placebo date
Rescue medication	The following prohibited medications will be considered as rescue medication when administered to subjects not responding to IMP or placebo: 

▪ Any systemic or local therapy with corticosteroids (other than the study drug) or immunosuppressant (except pre-surgical and/or surgical administration of 1 drop of a topical NSAID or corticosteroid, at the investigator discretion)

▪ Any topical ocular medication (except preservative-free antibiotics for prophylactic purposes and preservative-free artificial tears)

	

▪ Any systemic NSAID or opioids drugs (except occasional use of OTC formulations titrated no more than one single dose per week)

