### 6.3.8 Exposure to Treatment

Subjects will record each IMP or placebo administration (e.g., one drop every six hours, during 14 days) on their dispensed diaries.

Compliance is defined as the percentage of actual doses the patient instilled with respect to the number of total doses planned. The planned dose is always one drop of IMP or placebo. Compliance will be summarized categorically (<80%, ≥80% and 100%) by treatment regime. It will be calculated as follows:

Compliance of IMP/Placebo administered % = (num. of doses instilled / num. of planned doses) )(ml))\*100

Planned doses=56

Compliance at last visit with IMP/Placebo is defined as the percentage of actual doses the patient instilled with respect to the number of total doses planned at the time of the last visit with IMP/Placebo.

Compliance of IMP/Placebo administered % at last visit with IMP/Placebo = (num. of doses instilled / num. of planned doses at last visit with IMP/Placebo))(ml)\*100

Planned doses at last visit with IMP/Placebo = (End date IMP/Placebo exposure – First date IMP/Placebo exposure)\*4.

Compliance at visit 3 (day 8±1) is defined as the percentage of actual doses the patient instilled with respect to the number of total doses planned at visit 3.

Compliance of IMP/Placebo administered % at visit 3= (num. of doses instilled / num. of planned doses at visit 3 )(ml)\*100

Planned doses at visit 3=32

In case a scheduled dose was not administered (missed) the missed dose and the reason will be captured in the eCRF as per the patient diary and tabulated by treatment regimen.

All compliance data will be summarized and listed for the SAF.

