### 6.3.10 Adverse Events

AEs data are collected on the 'Adverse Events' eCRF form.

AEs will be coded according to the Medical Dictionary for Regulatory Activities (MedDRA) system, the latest version and tabulated by System Organ Class (SOC) and by Preferred Term (PT).

A Treatment-Emergent Adverse Event (TEAE) is defined as an AE observed after starting administration of IMP or placebo (see Section 6.3.1).

TEAEs will be summarized by presenting, for each treatment regimen, the number of events and the number and percentage of patients with:

- Any TEAE
- Any Serious Treatment Emergent Adverse Event (STEAE)
- Any TEAE of Special Interest (TEAESI)
- Any TEAE related to IMP/Placebo
- Any TEAE leading to treatment discontinuation (drug withdrawn)
- Any STEAE related to IMP/Placebo
- Any TEAESI related to IMP/Placebo

The number and percentage of TEAEs by causality and the number and percentage of mild moderate and severe TEAEs will be tabulated by SOC, PT and treatment arm. All tables with TEAEs by SOC and PT stratified by treatment regimen will only be counted by patient once within each PT.

The following tables will be provided with TEAEs by SOC and PT stratified by treatment regimen: TEAEs, TEAEs related to IMP/Placebo, TEAEs leading to discontinuation, STEAEs, STEAEs related to IMP/Placebo, TEAESI and TEAESIs related to IMP/Placebo.

TEAEs, STEAEs and TEAESIs will be tabulated by severity (mild, moderate or severe) and relationship to treatment (No: not related, unlikely related, Yes: possible, probable and certain). If a patient has more than one event with the same PT, the AE will only be counted once and the worst/maximal severity and the worst/strongest relationship will be used.

A listing of all AEs will be presented, whether treatment emergent or not. TEAEs will be flagged in this listing. A separate listing for deaths, STEAEs, AESIs and TEAEs leading to discontinuation will be provided (if any).

The following AEs (SOC, PT) of special interest (AESI) will be evaluated by Investigators at all study visits and time points (as applicable):

- IOP rise over 30 mmHg (SOC- INVESTIGATIONS, PT-INTRAOCULAR PRESSURE INCREASED)
- Pain/discomfort associated with IMP instillation (SOC-EYE DISORDERS, PT-EYE PAIN, OCULAR DISCOMFORT and related with IMP)

SAF will be used for all AE related summaries.

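### The SAP's mid-month and 1 July imputation of incomplete AE start dates classes many on-treatment events as not treatment-emergent, depending only on the calendar date of first dose

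*SAP*

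**What the plan says.** SAP 6.6 foresees no imputation of missing data in general, but it does complete partial dates where they are needed "for calculation / sorting / assignation based on dates". With month and year known: "if the month and year are available: Day “15” will be imputed". With less: "if only the year is available: Day “01” and month of “July” will be imputed". With no part known, nothing is imputed.

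SAP 6.3.1 gives the treatment-emergent test as a date window: "First dose IMP/Pacebo date ≤ start date AE ≤ last dose IMP/Placebo date". SAP 6.3.10 describes the same concept in words and refers back to 6.3.1: "A Treatment-Emergent Adverse Event (TEAE) is defined as an AE observed after starting administration of IMP or placebo".

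The window is short. Protocol 6.2.2 gives "one drop (0.03 mL) of IMP into the affected eye QID for a 14-day treatment period", and SAP 6.3.8 has "Planned doses=56".

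Medications have their own partial-date rules in SAP 6.3.9. One of them treats a medication started in the month of first dose as concomitant. SAP 6.3.10 has no counterpart for AEs.

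The ten AE tables in SAP 8.1 (14.3.1.1 to 14.3.1.10) are all restricted to treatment-emergent events. Other AEs appear only in listings. Protocol 9.1.13 also plans totals and tabulations of all AEs, but the SAP output list has no such table.

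**The concern.** A mid-month date is a reasonable midpoint for computing a duration. It is a poor choice for deciding whether an event falls inside a two-week window, because the answer then depends on where the 15th lies relative to first dose, which has no clinical meaning.

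Take a patient first dosed on 20 March 2020 with the last dose on Day 14, 2 April. An AE that began on 25 March but is recorded only as March becomes 15 March, before first dose. An AE that began on 1 April but is recorded only as April becomes 15 April, after last dose. Both were on treatment, both fail the window, and both leave all ten AE tables, including those for events of special interest, related events and discontinuations.

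The SAP also becomes inconsistent with itself. A drug started in March to treat the first of these AEs would be concomitant under 6.3.9, while the AE it treats would not be treatment-emergent. The AE was observed after dosing began, so it meets the wording of 6.3.10 but fails the formula to which that section refers.

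**Working it through.** The plan states no figure on this point, so there is none to reproduce. The check is a full enumeration of dates.

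**Inputs**
- Imputed start: 15th of the recorded month, or 1 July of the recorded year (SAP 6.6).
- Test: first dose ≤ start ≤ last dose (SAP 6.3.1).
- Treatment length: 14 days, 14 × 4 = 56 doses (protocol 6.2.2, SAP 6.3.8). Last dose is on Day 14, or on Day 15 if fewer than four doses are taken on Day 1. Both are shown.
- Assumption: first doses are spread evenly over the 366 dates of 2020, and on-treatment onset evenly over the treatment days. Protocol 4.3.3 expects the study to run from 1Q to 4Q 2020, with no accrual pattern given.

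**Month and year known, true onset on treatment**
- First dose on the 16th or later (186 of 366 dates, 50.8%): same-month onset is set before first dose. Next-month onset is set to the 15th, but the last dose falls on the 13th at the latest (14th if Day 15). Lost: 186 × 14 = 2604 of 2604, or 186 × 15 = 2790 of 2790.
- First dose on the 2nd to 15th: the whole treatment period lies in one month and contains the 15th. None is lost.
- First dose on the 1st (12 dates): with last dose on Day 14 the window ends on the 14th, so 12 × 14 = 168 are lost. With Day 15, none.
- Overall, Day 14: (2604 + 168) / (366 × 14) = 2772 / 5124 = 54.1%.
- Overall, Day 15: 2790 / (366 × 15) = 2790 / 5490 = 50.8%.
- Restricting first doses to 1 March to 30 November 2020 still gives 54% for Day 14.

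**Only the year known**
- 1 July lies in the window only for first doses from 18 June to 1 July (14 dates), or from 17 June (15 dates). Lost: 352 / 366 = 96.2%, or 351 / 366 = 95.9%. Day of the month plays no general part here.

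**No part known**
- There is no date to put into the formula, and the SAP does not say how the AE is then classed. Read literally, it cannot meet the test.

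**Reverse error, month and year known**
- Onset 1 to 7 days before first dose becomes treatment-emergent if it is in the same month and first dose is on day d = 2 to 15. Per month: the sum of min(7, d − 1) = 21 + 56 = 77. Over the year: 12 × 77 = 924 of 366 × 7 = 2562, or 36.1%.
- Onset after last dose up to Day 29: 27.4% become treatment-emergent with last dose on Day 14, and 29.4% with Day 15.

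**With both window bounds kept and an AE excluded only when its known month rules out the window**
- On-treatment AEs lost: 0 of 5124 (Day 14) and 0 of 5490 (Day 15).
- Month-only AEs from the 7 days before first dose counted as treatment-emergent: 12 × 21 + 7 × (366 − 84) = 2226 of 2562, or 86.9%.
- Month-only AEs after last dose up to Day 29 so counted: 73.8% (Day 14) and 75.4% (Day 15).

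**The case against.** The strongest reply concerns reach. Protocol 8.3.3 requires date and time of onset for every AE, and 8.3.7 requires a start date. Protocol 10.6 provides for data queries, and the rule applies only to what is still incomplete afterwards. Post-dose visits are at Days 3, 8, 15 and 29, so recall intervals are short. The initial SAE report must give the event's start date (8.3.5), and events of special interest must be reported within 24 hours (8.3.9). Year-only dates are unlikely in a study of about five weeks. All of this stands: the percentages are shares of a number that the documents do not give and that may be small or zero.

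The reply on consequence also stands. The rule is the same in both arms, SAP 6.3.10 compares safety descriptively only, and no efficacy result is touched.

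The reply on remedy stands in part. A rule that counts every AE whose onset might be on or after first dose would drop the last-dose bound and so change the definition of a treatment-emergent event. A rule that depends on the visit of first report would rely on an item that protocol 8.3.3 and 8.3.7 do not list among the AE fields. Even that visit would not settle onset at Visit 1, because protocol 4.3.2.2 places the AE assessment there after dosing. The correction must keep both bounds and state its own cost.

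None of this rescues the rule. Where a partial AE date does remain, the plan prescribes a definite classification, and that classification is often wrong.

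**Conclusion.** The concern holds as a minor defect in a stated rule. Among on-treatment AEs whose start is still known only to the month after data management, all are lost from the treatment-emergent set for patients first dosed on the 16th or later. Overall this is 54% of such AEs, or 51% with last dose on Day 15. With only the year known, about 96% are lost. In the other direction, about 36% of month-only AEs from the week before first dose and 27% to 29% of those after last dose up to Day 29 enter the treatment-emergent set. These shares assume evenly spread first doses and onsets.

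Four stronger readings are tempting, and the documents do not support them.
- That half of all AEs are affected: the shares apply only to partially dated AEs.
- That events disappear from the report: they leave Tables 14.3.1.1 to 14.3.1.10, but SAP 6.3.10 lists all AEs, SAP 6.6 shows their dates as recorded, and protocol 9.1.13 still plans all-AE tabulation.
- That the rule favours clobetasol: it is identical in both arms, so it distorts treatment-emergent frequencies and need not bias the comparison.
- That the after-the-15th condition describes both imputations: the 1 July rule loses events for nearly every first-dose date.

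**What to change.** Add an AE-specific rule to SAP 6.6. An AE with an incomplete or missing start date is treatment-emergent unless the known parts of that date, the AE end date or other recorded data (for example, that it was recorded at the screening visit) show onset before first dose or after last dose. Keep both bounds of the SAP 6.3.1 window, so that the definition itself is unchanged. Keep Day 15 and 1 July for non-safety calculations only.

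Add the all-AE tabulation planned in protocol 9.1.13 to the output list in SAP 8.1, so that an AE classed as not treatment-emergent still appears in a table.

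The wording costs two or three sentences and one table. The statistical cost is overcounting in both arms: by date parts alone, up to about 87% of month-only AEs from the 7 days before first dose, and about 74% to 75% of those after last dose up to Day 29, would count as treatment-emergent. End dates and other recorded data would lower these shares. For safety reporting this is the more cautious direction of error, and it removes the loss of on-treatment events.
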